6.2.2 Timing of Dose Administration

Trial treatment should be administered on Day 1 of each cycle after all procedures/assessments have been completed as detailed on the Trial Flow Chart (Section 7.0). Trial treatment may be administered up to 3 days before or after the scheduled Day 1 of each cycle due to administrative reasons.

All trial treatments will be administered on an outpatient basis.

Pembrolizumab will be administered as a 30 minute IV infusion (treatment cycle intervals may be increased due to toxicity as described in Section 6.2.1.2). Every effort should be made to target infusion timing to be as close to 30 minutes as possible. However, given the variability of infusion pumps, a window of -5 minutes and +10 minutes is permitted (i.e., infusion time is 30 minutes: -5 min/+10 min).

The specific instructions for pembrolizumab dose calculation, reconstitution, preparation of the infusion fluid, and administration will be provided by the Drug Manufacturer in conjunction with pembrolizumab.

6.2.3 Trial Blinding/Masking

This is an open-label trial; therefore, the Drug Manufacturer, investigator and subject will know the treatment administered.

6.3 Randomization or Treatment Allocation

There will be no randomization. For Part A all patients that meet eligibility criteria will be enrolled. For Part B PD-L1 expression pre-screening will be performed using a CLIA approved immunohistochemistry assay, performed centrally via a commercial provider using the proprietary 22C3 antibody. Estimated turnaround time will be 1-2 weeks. Results will be classified based on prior data (Part A +/- data for Mesothelioma patients from the Keynote 28 study) into above or below the optimal threshold, and patients with tumor PD-L1 expression equal or above the threshold will be eligible to enroll in Part B (See Schema Section 3.2):

6.4 Transition from Part A to Part B

If Part A meets efficacy criteria outline in the statistical section, determination of correlation of PD-L1 expression with response and optimal threshold will be performed. Such a threshold would be employed as a selection criterion for Part B. Should no correlation be present or no clinically reasonable threshold be identifiable, the protocol ideally after discussion with the drug manufacturer (Merck) may proceed to part B without a threshold, or an alternative biomarker for enrichment may be implemented if mutually agreed and felt to be clinically reasonable and/or superior to PD-L1 expression.

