6.13.4 Nanostring Analysis

From 3-5 FFPE slides RNA will be extracted using the Qiagen RNA/DNA FFPE kit and protocol. A Nanostring probeset including ca 20-150 immune and other marker related probes will be used using the Nanostring (Seattle) standard ordering and analysis process. The

Nanostring nCounter available in the [name] lab at the University of Chicago will be used. Alternatively FFPE based RNAseq libraries may be constructed using the Illumina FFPE RNA access protocol. The [name] lab is experienced with both the Nanostring and FFPE RNAseq process and additional details are available on request. These are exploratory analyses and laboratory protocols are constantly updated.

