Based on the results from Part A - we will use the Youden Index (Youden 1950; Fluss et al., 2005) methodology to determine the optimal threshold for PD-L1 expression in correlation with tumor response, and if a correlation is identified we will use this threshold for Part B. The Youden index is the maximum value of the sum of sensitivity (here the proportion of responders with a PD-L1 expression level above a given cutpoint) and specificity (proportion of non-responders below the cutpoint) (minus one) over all threshold values (scored 0-100% for the 22C3 antibody based IHC assay) of the biomarker. Since we anticipate only about 4 responders in part A, the threshold will also be assessed/validated in a second cohort of Mesothelioma patients from the Keynote 28 study as available. The overall ability of PD-L1 to predict response will be assessed using the area under the ROC curve (AUC). If the area is significantly greater than 0.5, we will proceed to part B using the optimum cutpoint as determined from the Youden index. Our sample size of $n=35$ patients will provide 80% power if the true AUC is 0.81, based on a one-sided test at the $\alpha=0.10$ significance level (Hanley and McNeil, 1983). Should no statistically significant correlation be identified alternative biomarkers will be assessed as possible candidates and the study will proceed to part B as an expansion cohort without pre-screening.

For part B the null hypothesis that the true response rate (in a PD-L1 preselected population is 10% [p_0]) will be tested against a one-sided alternative of 25% [p_A]. 30 patients will be accrued. If there are fewer than 6 responses in these 30 the null hypothesis will be accepted. The null hypothesis will be rejected if 6 or more responses are observed in 30 patients. This design yields a type I error rate of 0.1 and power of 80% when the true response rate is 25%.

A response rate of 25% would be considered clinically very meaningful for MM and suggest that development of pembrolizumab in such a PD-L1 preselected population would potentially be competitive with upfront or 2nd line chemotherapy.

Secondary Objectives

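### Sections 6.4 and 9.5 disagree on how Part B enrolls if PD-L1 fails, and 6.4 lets a substitute marker select patients without the statistical test that PD-L1 must pass

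*Combined protocol and SAP*

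**What the plan says.** **PD-L1.** Section 9.5 gives PD-L1 a formal gate: "If the area is significantly greater than 0.5, we will proceed to part B using the optimum cutpoint", with the cutpoint taken from the Youden index. The test is one-sided at 0.10, and the sample of 35 "will provide 80% power if the true AUC is 0.81, based on a one-sided test at the" that level. About 4 responders are expected; 3 are enough to open Part B.

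**If PD-L1 fails, section 9.5.** "alternative biomarkers will be assessed as possible candidates and the study will proceed to part B as an expansion cohort without pre-screening". Other markers may be examined, but Part B is unselected.

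**If PD-L1 fails, section 6.4.** The trigger is worded differently: "Should no correlation be present or no clinically reasonable threshold be identifiable". One option is then to run Part B with no marker cutoff. The other is this: "an alternative biomarker for enrichment may be implemented if mutually agreed and felt to be clinically reasonable and/or superior to PD-L1 expression". No metric, significance level, cutpoint method, candidate list or validation step is given.

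**Part B test.** The 10% null in 9.5 is stated for a PD-L1 preselected population. No null is given for selection on another marker or for no selection.

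**The concern.** The two sections can produce different Part B populations from the same Part A data. Under 6.4, the prespecified marker faces a statistical bar that an unnamed replacement does not. Because the clause says and/or, a judgement of clinical reasonableness is enough and superiority need not be shown.

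Where superiority is claimed, it would rest on the same 35 patients and 3–4 responders, with PD-L1 as a comparator already known to have done poorly. A marker unrelated to response can easily look better in that setting. If it were adopted, patients would be turned away for no reason, and the result would be described as efficacy in a selected population.

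**Working it through.** **1. The plan's own figure.** Inputs from 9.5: n = 35, 4 responders (so 31 non-responders), true AUC 0.81, one-sided 0.10. The Hanley–McNeil variance is SE² = [A(1−A) + (n₁−1)(Q₁−A²) + (n₀−1)(Q₂−A²)]/(n₁n₀), with Q₁ = A/(2−A) and Q₂ = 2A²/(1+A).

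- At A = 0.5: SE₀ = √(3.0/124) = 0.1555. The critical AUC is 0.5 + 1.2816 × 0.1555 = 0.70.
- At A = 0.81: SE₁ = 0.1360.
- Power = Φ((0.31 − 0.1993)/0.1360) = Φ(0.81) = 79%. The stated 80% reproduces. With 3 responders it is 70%.

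**2. How often would a noise marker look superior?** Simulation of 35 patients with 3 or 4 responders and normally distributed markers. PD-L1 counts as failed if its AUC is at or below the one-sided 0.10 limit. The alternatives are unrelated to response and to PD-L1, with direction fixed beforehand. Entries are the share of failed-PD-L1 trials in which the (best) alternative has the higher AUC. Neither the number of candidates nor PD-L1's true AUC is in the documents, so both are shown as ranges.

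| PD-L1 true AUC | 1 marker | best of 5 | best of 10 |
|---|---|---|---|
| 0.50 | 54% | 90% | 97% |
| 0.60 | 42–43% | 83–84% | 94% |
| 0.70 | 31–34% | 75–77% | 90–91% |
| 0.81 | 24–26% | 67–69% | 86–87% |

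**3. Correlated markers.** With a common correlation of 0.5 and PD-L1 truly uninformative, the figures barely change: 53%, 87% and 94%. If PD-L1's true AUC is 0.81 and the correlation is 0.5, the best of 5 wins in only about 17–26% of trials.

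**4. Would copying the PD-L1 test across be enough?** One noise marker passes about 10–11% of the time. At least one of several independent ones passes with nominal probability 1 − 0.9⁵ = 41% (k = 5) or 1 − 0.9¹⁰ = 65% (k = 10); simulation gives 43% and 68%. So an adjustment is needed. With a Bonferroni correction and 4 responders the observed AUC would have to exceed 0.5 + 2.054 × 0.1555 = 0.82 (k = 5) or 0.5 + 2.326 × 0.1555 = 0.86 (k = 10).

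**5. Effect on Part B.** P(X ≥ 6 | n = 30, p) is 0.073 at p = 10%, 0.143 at p = 12% (Part A's target rate) and 0.797 at p = 25%. These depend only on the true rate in the patients enrolled. Part B is a fresh cohort, so selecting on a noise marker leaves the test's error rate where it was.

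**The case against.** The strongest reply is that 6.4 is not an algorithm. It permits an alternative marker, does not mandate one, and makes mutual agreement a condition alongside the clinical judgement. It names no AUC comparison and no search for the best of several candidates, so step 2 illustrates what the clause leaves open; it does not simulate a stated rule. That stands. A reader might infer that almost any noise marker would qualify. The documents do not support this: agreement is required, and a single pre-chosen noise marker outranks a failed PD-L1 about half the time at most.

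The candidate pool can also be overstated. Section 6.13.4 plans 20–150 expression probes, but calls the work exploratory, and 9.5 reduces the T-cell inflamed phenotype to one existing signature. The SNP work depends on prior confirmation in another cohort, and several assays run only where tissue allows. The probe count should not be read as 150 enrichment candidates.

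Third, 9.5 already sends a non-significant PD-L1 result to an unselected Part B, and the eligibility and allocation text (6.1.1, 6.3) names only PD-L1. That is a good reason to let 9.5 govern, but it does not remove the permission in 6.4.

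Last, a formal adjusted test is costly in power. With 4 responders, a genuine marker with AUC 0.81 would be correctly selected about 53–56% of the time among 5 candidates and 39–46% among 10, against about 82% if tested alone. This is a fair argument for simply dropping the substitute route.

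**Conclusion.** The point holds as a conflict between two sections and a missing criterion in one of them. The conflict needs no assumption: for a non-significant PD-L1 result, 9.5 says no pre-screening and 6.4 also allows enrichment on another marker.

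The size of the risk does rest on assumptions. With 3–4 responders and independent markers, an uninformative alternative would outrank a failed PD-L1 in about 25–54% of trials if one is chosen beforehand, and in about 67–97% if the best of 5–10 is taken. The lower ends apply when PD-L1's true AUC is 0.81, the upper ends when it is 0.50. Correlation with an informative PD-L1 can bring the figures well below these.

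A reader might also infer that Part B's type I error is inflated. It is not. The harm is needless exclusion of patients, and a claim about a selected population tested against a null that was set for a different one.

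**What to change.** 1. Reword 6.4 to match 9.5, with one shared definition of PD-L1 failure that also covers the case of no usable threshold: Part B then opens without pre-screening.
2. If enrichment on an alternative marker is kept, write it into both sections. Name a short list of markers with expected directions before response is linked to marker data. Require a one-sided 0.10 AUC test adjusted for the number of candidates, and state the cutpoint rule. A max-statistic permutation test among patients with the markers measured is one suitable choice; other adjustments would also serve. If nothing passes, Part B is unselected.
3. State the Part B null rate for each population that could be enrolled. This is needed even under 9.5's own route: the unselected null in Part A is 2%, while Part B's 10% is given only for PD-L1 selection.

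The cost is wording in 6.4 and 9.5, plus a short program if option 2 is used; no added patients or assays. The downside is that, with about 4 responders, a true alternative marker will often fail to qualify, and the sponsor gives up discretion to enrich on judgement.

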6.5 Optional continuation of treatment beyond progression

In order to ensure that patients are not exposed to unreasonable risk by continuing a potentially ineffective therapy in spite of disease progression, the following procedures are put into place:

In subjects who have initial evidence of radiological PD, there is the option to continue a subject on study treatment until repeat imaging is obtained a minimum of 4 weeks later or beyond. A supplemental consent form is available and required for this purpose and it is at the discretion of the treating physician whether to consider continuing pembrolizumab therapy.

This decision should be based on the clinical judgment of the subject's overall clinical condition, including performance status, clinical symptoms, and laboratory data.

Subjects may receive treatment if they have signed the supplemental consent form and are clinically stable as defined by the following criteria:

- Absence of signs and symptoms indicating disease progression
- No decline in ECOG performance status (ECOG 0 or 1 required)
- Absence of rapid progression of disease
- Absence of progressive tumor at critical anatomical sites (e.g., cord compression, development or worsening of brain metastases, respiratory failure from tumor compression, etc.) requiring urgent alternative medical intervention
- Demonstrate adequate organ function as defined in Table 1 (section 6.1.2)

Patients must have signed the supplemental consent form for continuation of therapy beyond progression. Treatment beyond initial evidence of tumor progression is not the standard of care, although commonly used in trials with PD-1 and PD-L1 inhibitors. The supplemental consent form outlines the potential risks of continuing therapy (namely further worsening of the disease), and lists alternative treatment options, namely participation in another clinical trial, off label use of chemotherapy, or comfort care, as no other FDA approved agents are available after prior failure of methotrexate/platinum.

When feasible, subjects should not be discontinued until progression is confirmed. This allowance to continue treatment despite initial radiologic progression takes into account the observation that some subjects can have a transient tumor flare in the first few months after the start of immunotherapy, but with subsequent disease response. Subjects that are deemed clinically unstable are not required to have repeat imaging for confirmation of progressive disease. Supportive retrospective central review of all imaging time-points will be performed for this study using modified RECIST criteria for mesothelioma (Byrne et al 2004).

In addition some patterns of benefit may not be captured by traditional assessment of progressive disease (e.g. oscillating patterns of tumor shrinkage and regression have been

observed in patients on PD-1/PD-L1 agents (Chen et al, CRI meeting 2014). In patients deemed to have clinical benefit/symptomatic improvement (and fulfillment of all of the above criteria), further continuation of therapy can be approved by the PI.

6.6 Stratification

No stratification will be done.

6.7 Concomitant Medications/Vaccinations (allowed & prohibited)

Medications or vaccinations specifically prohibited in the exclusion criteria are not allowed during the ongoing trial. If there is a clinical indication for one of these or other medications or vaccinations specifically prohibited during the trial, discontinuation from trial therapy or vaccination may be required. The investigator should discuss any questions regarding this with the Drug Manufacturer. The final decision on any supportive therapy or vaccination rests with the investigator and/or the subject's primary physician. However, the decision to continue the subject on trial therapy or vaccination schedule requires the mutual agreement of the Investigator, the Drug Manufacturer, and the subject.

6.7.1 Acceptable Concomitant Medications / Radiation

All treatments that the investigator considers necessary for a subject's welfare may be administered at the discretion of the investigator in keeping with the community standards of medical care. All concomitant medication will be recorded on the case report form (CRF) including all prescription, over-the-counter (OTC), herbal supplements, and IV medications and fluids. If changes occur during the trial period, documentation of drug dosage, frequency, route, and date may also be included on the CRF.

All concomitant medications received within 28 days before the first dose of trial treatment and 30 days after the last dose of trial treatment should be recorded. Concomitant medications administered after 30 days after the last dose of trial treatment should be recorded for SAEs and ECIs as defined in Section 7.2.

Radiation for selected tumor lesions/tumors may be administered concurrently with pembrolizumab treatment, e.g. for progressive lesions causing symptoms such as pain.

6.7.2 Prohibited Concomitant Medications

Subjects are prohibited from receiving the following therapies during the Screening and Treatment Phase (including retreatment for post-complete response relapse) of this trial:

- Anti-cancer systemic chemotherapy or biological therapy
- Immunotherapy not specified in this protocol
- Chemotherapy not specified in this protocol
- Investigational agents other than pembrolizumab

- Radiation therapy
 - Note: Radiation therapy to a symptomatic solitary lesion or to the brain may be allowed after consultation with the PI.
- Live vaccines within 30 days prior to the first dose of trial treatment and while participating in the trial. Examples of live vaccines include, but are not limited to, the following: measles, mumps, rubella, chicken pox, yellow fever, rabies, BCG, and typhoid (oral) vaccine. Seasonal influenza vaccines for injection are generally killed virus vaccines and are allowed; however intranasal influenza vaccines (e.g. Flu-Mist®) are live attenuated vaccines, and are not allowed.
- Glucocorticoids for any purpose other than to modulate symptoms from an event of clinical interest of suspected immunologic etiology. The use of physiologic doses of corticosteroids may be approved after consultation with the Drug Manufacturer.

Subjects who, in the assessment by the investigator, require the use of any of the aforementioned treatments for clinical management should be removed from the trial. Subjects may receive other medications that the investigator deems to be medically necessary.

The Exclusion Criteria describes other medications which are prohibited in this trial.

There are no prohibited therapies during the Post-Treatment Follow-up Phase.

6.8 Rescue Medications & Supportive Care

6.8.1 Supportive Care Guidelines

Subjects should receive appropriate supportive care measures as deemed necessary by the treating investigator including but not limited to the items outlined the appendix 13.3.16 Events of Clinical Interest (ECI) Guidance Section of this protocol.

6.9 Diet/Activity/Other Considerations

6.9.1 Diet

Subjects should maintain a normal diet unless modifications are required to manage an AE such as diarrhea, nausea or vomiting.

6.9.2 Contraception

Pembrolizumab may have adverse effects on a fetus in utero. Furthermore, it is not known if pembrolizumab has transient adverse effects on the composition of sperm. Female subjects of childbearing potential should be willing to use 2 methods of birth control or be surgically sterile, or abstain from heterosexual activity for the course of the study through 120 days

after the last dose of study medication. Subjects of childbearing potential are those who have not been surgically sterilized or have not been free from menses for > 1 year.

The two birth control methods can be either two barrier methods, or a barrier method plus a hormonal method to prevent pregnancy. Subjects should start using birth control from study Visit 1 throughout the study period up to 120 days after the last dose of study therapy.

The following are considered adequate barrier methods of contraception: diaphragm, condom (by the partner), copper intrauterine device, sponge, or spermicide. Appropriate hormonal contraceptives will include any registered and marketed contraceptive agent that contains an estrogen and/or a progestational agent (including oral, subcutaneous, intrauterine, or intramuscular agents).

Subjects should be informed that taking the study medication may involve unknown risks to the fetus (unborn baby) if pregnancy were to occur during the study. In order to participate in the study they must adhere to the contraception requirement (described above) for the duration of the study and during the follow-up period defined in section 8.2.2-Reporting of Pregnancy and Lactation to Merck. If there is any question that a subject will not reliably comply with the requirements for contraception, that subject should not be entered into the study.

6.9.3 Use in Pregnancy

If a subject inadvertently becomes pregnant while on treatment with pembrolizumab, the subject will immediately be removed from the study. The site will contact the subject at least monthly and document the subject's status until the pregnancy has been completed or terminated. The outcome of the pregnancy will be reported to Merck without delay and within 24 hours if the outcome is a serious adverse experience (e.g., death, abortion, congenital anomaly, or other disabling or life-threatening complication to the mother or newborn). The study investigator will make every effort to obtain permission to follow the outcome of the pregnancy and report the condition of the fetus or newborn to Merck. If a male subject impregnates his female partner the study personnel at the site must be informed immediately and the pregnancy reported to Merck and followed as described above and in Section 8.2.2.

6.9.4 Use in Nursing Women

It is unknown whether pembrolizumab is excreted in human milk. Since many drugs are excreted in human milk, and because of the potential for serious adverse reactions in the nursing infant, subjects who are breast-feeding are not eligible for enrollment.

6.10 Subject Withdrawal/Discontinuation Criteria

Subjects may withdraw consent at any time for any reason or be dropped from the trial at the discretion of the investigator should any untoward effect occur. In addition, a subject may be withdrawn by the investigator or the Drug Manufacturer if enrollment into the trial is

inappropriate, the trial plan is violated, or for administrative and/or other safety reasons. Specific details regarding discontinuation or withdrawal are provided in Section 8.1.4 – Other Procedures.

A subject must be discontinued from the trial for any of the following reasons:

- The subject or legal representative (such as a parent or legal guardian) withdraws consent.
- Confirmed radiographic disease progression

Note: For unconfirmed radiographic disease progression, please see Section 6.5.

Note: A subject may be granted an exception to continue on treatment with confirmed radiographic progression if clinically stable or clinically improved, please see Section 6.5

- Unacceptable adverse experiences (See Section 13)
- Intercurrent illness that prevents further administration of treatment
- Investigator's decision to withdraw the subject
- The subject has a confirmed positive serum pregnancy test
- Noncompliance with trial treatment or procedure requirements
- The subject is lost to follow-up
- Completed 24 months of treatment with pembrolizumab

Note: 24 months of study medication is calculated from the date of first dose. Subjects who stop pembrolizumab after 24 months may be eligible for up to one year of additional study treatment if they progress after stopping study treatment provided they meet the requirements detailed in Section 8.1.5.2.1.

- Administrative reasons

The End of Treatment and Follow-up visit procedures are listed in Section 7 (Protocol Flow Chart) and Section 8.1.5 (Visit Requirements). After the end of treatment, each subject will be followed for 30 days for adverse event monitoring (serious adverse events will be collected for 90 days after the end of treatment as described in Section 8.2.3.1). Subjects who discontinue for reasons other than progressive disease will have post-treatment follow-up for disease and clinical evaluation until disease progression, initiating a non-study cancer treatment, withdrawing study consent or becoming lost to follow-up. After documented

disease progression each subject will be followed by telephone for overall survival until death, withdrawal of consent, or the end of the study, whichever occurs first.

Procedures for currently enrolled patients with a history of pneumonitis

Subjects who are currently enrolled and have a history of pneumonitis may either discontinue pembrolizumab or continue dosing with pembrolizumab at the discretion of the treating physician after discussion of the safety information and informed consent.

